5.1.4 Trial Treatments

The treatment to be used in this trial is outlined below in Table 3. Each cycle is 21 days in length.

Table 3 Trial Treatments

Drug	Dose/Potency	Dose Frequency	Route of Administration	Regimen/Treatment Period	Use
MK-3475	200 mg	Q3W	IV infusion	Day 1 of each cycle	Experimental

Afatinib*	20 mg, 30 mg, or 40 mg	Once daily	Oral	Day 1-21 of each cycle	Experimental
The MK-3475 dosing interval may be increased due to toxicity as described in Section 5.1.5.3.					
*Cohort B begins in Cycle 3					

Table 4: Dose De- Escalation Schema

Dose Level	Number of Patients	Afatinib (Daily)	MK-3475 (q3 weeks)
0	3+	40 mg D1	200 mg D1
-1	3+	30 mg D1	200 mg D1
-2	3+	20 mg D1	200 mg D1

Each cycle is 21 days in length.

Dose De-Escalation

This treatment will start at dose level 0 (Bold). Afatinib is an oral agent that will be given once daily for 21 days per cycle starting on day 1 of each cycle before administration of MK-3475. It should be taken in the morning with 200 mL of water. Tablets should be taken 1 hour before or 2 hours after meals. MK-3475 will be given once every 3 weeks at a fixed dose of 200 mg. Treatment will be administered until progression or toxicity or withdrawal of consent as defined in this protocol.

Cohort A (Arm A): Dose Expansion

This treatment will start at the MTD determined in the dose de-escalation portion of this trial. Afatinib is an oral agent that will be given once daily for 21 days per cycle starting on day 1 of each cycle before administration of MK-3475. It should be taken in the morning with 200 mL of water. Tablets should be taken 1 hour before or 2 hours after meals. MK-3475 will be given once every 3 weeks. Treatment will be administered until progression or toxicity or withdrawal of consent as defined in this protocol.

Cohort B (Arm B): Dose Expansion

This treatment will start at the MTD determined in the dose de-escalation portion of this trial. MK-3475 will be administered on Day 1 of each cycle, which is q21d in length. Afatinib is an oral agent that will be given once daily for 21 days per cycle starting on Cycle 3 Day 1 of each cycle starting prior to administration of MK-3475 on day 1. It should be taken in the morning with 200 mL of water. Tablets should be taken 1 hour before or 2 hours after meals. MK-3475 will be given once every 3 weeks. Treatment will be administered until progression or toxicity or withdrawal of consent as defined in this protocol.

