5.1.5.2 Dose De-Escalation

Dose Level	Number of Patients	Afatinib (Daily)	MK-3475 (q3 weeks)
0	3+	40 mg D1	200 mg D1
-1	3+	30 mg D1	200 mg D1
-2	3+	20 mg D1	200 mg D1

Figure 1: Dose De-Escalation Schema

This is a phase I study. A minimum of 9 patients (if trial is terminated early due to unacceptable toxicity and a maximum of 38 patients (18 patients in the dose- de-escalation cohort plus 10 in each of the two expansion cohorts) are anticipated for this trial. Analysis of safety and biomarkers will be limited to patients who receive active treatment.

The dose-de-escalation phase will establish a MTD recommended dose of MK-3475 in expansion cohorts (A +B).

We plan to enter 3 patients at Dose Level 0. If 0/3 or 1/3 patients experience a DLT on level 0, an additional 3 patients will be accrued to Level 0, where 2 or more DLTs will terminate that study arm and we will proceed to dose level -1.

If 2 or more patients have DLTs at level 0, patients will be accrued at level -1. If 1/3 patients experience a DLT on level -1, an additional 3 patients will be accrued to Level -1, where 2 or more DLTs will require termination of that study arm while 1 DLT out of 6 will result in proceeding with dose level -1 as the MTD for the dose expansion cohorts.

If 2 or more patients have DLTs at level -1, patients will be accrued at level -2. If 1/3 patients experience a DLT on level -2, an additional 3 patients will be accrued to Level -2, where 2 or more DLTs will require termination of the study while 1 DLT out of 6 will result in proceeding with dose level -2 as the MTD for the dose expansion cohorts.

The phase I dose de-escalation portion of the trial will be closed when the maximum tolerated dose level (MTD) or dose level 0 is reached and six patients have been treated at that dose level.

Dose modifications for patients that experience DLT is described in section 5.1.5.3. Once the dose is decreased, there will be no dose re-escalation allowed for an individual patient.

The recommended phase II dose (RP2D) will be determined by the overall assessment of the MTD and toxicities observed in the de-dose escalation and dose expansion portion of this study.

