5.3 Definition of Dose Limiting Toxicities (DLT)

All toxicities will be graded using National Cancer Institute (NCI) CTCAE Version 4.0. The occurrence of any of the following toxicities during Cycle 1 will be considered a DLT, if judged by the Investigator to be possibly, probably or definitely related to study drug (either afatinib or MK-3475) administration:

1. Grade 4 non-hematologic toxicity (not laboratory).
2. Grade 4 hematologic toxicity lasting ≥ 14 days.
3. Grade 3 non-hematologic toxicity (not laboratory) lasting > 3 days despite optimal supportive care with maximal supportive care for diarrhea and rash. See description of maximal supportive care for diarrhea and rash attributed to afatinib below.
4. Any Grade 3 or Grade 4 non-hematologic laboratory value if:
 - Medical intervention is required to treat the patient, or
 - The abnormality leads to hospitalization, or
 - The abnormality persists as \geq grade 3 for > 1 week.
5. Febrile neutropenia Grade 3 or Grade 4:
 - Grade 3 is defined as ANC $< 1000/\text{mm}^3$ with a single temperature of > 38.3 degrees C (101 degrees F) or a sustained temperature of ≥ 38 degrees C (100.4 degrees F) for more than one hour
 - Grade 4 is defined as ANC $< 1000/\text{mm}^3$ with a single temperature of > 38.3 degrees C (101 degrees F) or a sustained temperature of ≥ 38 degrees C (100.4 degrees F) for more than one hour, with life-threatening consequences and urgent intervention indicated.
6. Thrombocytopenia $< 25,000/\text{mm}^3$ if associated with:
 - A bleeding event which does not result in hemodynamic instability but requires an elective platelet transfusion, or
 - A life-threatening bleeding event which results in urgent intervention and admission to an Intensive Care Unit
 - Grade 5 toxicity (i.e. death).
7. Diarrhea is an expected adverse event from afatinib. Diarrhea attributed to afatinib will be considered a DLT if grade 3 despite maximal medical management for > 72 hours. Maximal medical management will be defined as anti-diarrheal management that includes: loperamide, diphenoxylate and atropine, and tincture of opium. Grade 4 diarrhea will be considered a DLT.

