8. Acneiform rash is an expected adverse event from afatinib. Acneiform rash attributed to afatinib will be considered a DLT if grade 3 despite maximal medical management for > 72 hours. Maximal medical management will be defined as oral antibiotic, preferably doxycycline, cleocin solution or cream and topical steroids. In addition an asymptomatic/minimally symptomatic classic acneiform rash will only be considered a DLT if it covers \geq 50% BSA. Grade 4 rash will be considered a DLT.
9. To be evaluable for a DLT, 80% of dose must have been administered in cycle 1 unless a DLT occurred.
10. Delay in starting cycle 2 of \geq 14 days due to toxicity related to afatinib and/or MK-3475

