2. In general, the window for each visit is \pm 3 days unless otherwise specified.
3. For women of reproductive potential, a urine or serum pregnancy test will be performed within 72 hours prior to first dose of trial treatment. If urine pregnancy results cannot be confirmed as negative, a serum pregnancy test, performed by the local study site laboratory, will be required. Pregnancy tests (serum and/or urine tests) should be repeated if required by local guidelines.
4. Coagulation factors (PT/INR and aPTT) should be monitored closely throughout the trial for any subject receiving anticoagulant therapy.
5. Laboratory tests for screening are to be performed within 10 days prior to the first dose of trial treatment.
6. After Cycle 1, lab samples can be collected up to 72 hours prior to the scheduled time point. Laboratory results must be known and acceptable prior to dosing.
7. The initial tumor imaging will be performed within 30 days prior to the first dose of trial treatment. Scans performed as part of routine clinical management are acceptable for use as the screening scan if they are of diagnostic quality and performed within 30 days prior to the first dose of trial treatment. On-study imaging will be performed every 6 weeks (42 -7 days) after the first dose of trial treatment or more frequently if clinically indicated. The timing for imaging studies should follow calendar days and should not be adjusted for delays in cycle starts or extension of MK-3475/afatinib cycle frequencies. The same imaging technique should be used in a subject throughout the trial. CT including the chest, abdomen and pelvis or PET-CT is required for the baseline assessment.
8. Provide documentation of the subject's tumor EGFR mutation from a CLIA certified laboratory.
9. MK-3475 can be administered for up to 2 years. For the dose de-escalation and Cohort (Arm) A (concurrent afatinib and MK-3475) both drugs will be administered as outlined in this protocol starting with cycle #1. For cohort B. MK-3475 will be initiated with cycle #1 and afatinib will commence in combination with MK-3475 starting with cycle #3.
10. Tumor biopsy for immune and EGFR biomarker analysis will be performed prior to Cycle 1 of treatment either on archival tissue or fresh biopsy (within 60 days). Repeat biopsy will be performed prior to initiation of cycle 3 (42 days (-7 days))

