8.0 STATISTICAL ANALYSIS PLAN

8.1 Statistical Analysis Plan Summary

This is a phase I/Ib study. A minimum of 9 patients, if trial is terminated early due to unacceptable toxicity and a maximum of 38 patients (18 patients in the dose de-escalation cohort plus 10 in each of the two expansion cohorts) are anticipated for this trial. Analysis of safety and biomarkers will be limited to patients who receive active treatment.

The dose de-escalation phase will establish a MTD recommended dose of MK-3475 in combination with lead in MK-3475 followed by the combination or concurrent afatinib/MK-3475.

We plan to enter 3 patients at Dose Level 0. If 0/3 or 1/3 patients experience a DLT on level 0, an additional 3 patients will be accrued to Level 0, where 2 or more DLTs will terminate that study arm and we will proceed to dose level -1.

If 2 or more patients have DLTs at level 0, patients will be accrued at level -1. If 1/3 patients experience a DLT on level -1, an additional 3 patients will be accrued to Level -1, where 2 or more DLTs will require termination of that study arm while 1 DLT out of 6 will result in proceeding with dose level -1 as the MTD for the dose expansion cohorts.

If 2 or more patients have DLTs at level -1, patients will be accrued at level -2. If 1/3 patients experience a DLT on level -2, an additional 3 patients will be accrued to Level -2, where 2 or more DLTs will require termination of the study while 1 DLT out of 6 will result in proceeding with dose level -2 as the MTD for the dose expansion cohorts.

The phase I de-dose escalation portion of the trial will be closed when the maximum tolerated dose level (MTD) or dose level 0 is reached and six patients have been treated at that dose level.

Please see section 5.1.4.2 for further details.

All patients at a given dose level who have not experienced DLT, must be observed for a minimum of 21 days or until completion of their first cycle of therapy before the dose level can be escalated. Treatment will continue in an individual patient at the same dose level if no DLT is observed and if benefit is observed. There will be no dose escalation allowed for an individual patient.

The recommended phase II dose (RP2D) will be determined by the overall assessment of the MTD and toxicities observed in the de-dose escalation and dose expansion portion of this study.

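### The Cycle 1 DLT rules and the lead-in MTD statement do not fit Cohort B's Cycle 3 afatinib start, and A-versus-B toxicity is not aligned on combination exposure

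*Combined protocol and SAP*

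**What the plan says.** **DLT rules.** Section 5.3 opens with "The occurrence of any of the following toxicities during Cycle 1 will be considered a DLT" and names no phase or cohort. Item 9 adds "To be evaluable for a DLT, 80% of dose must have been administered in cycle 1 unless a DLT occurred". Item 10 counts as a DLT a "Delay in starting cycle 2 of" 14 days or more for related toxicity. Section 5.9 replaces DLT-free patients who received less than 80% of MK-3475 and afatinib in Cycle 1.

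**MTD statements.** Section 8.1 says de-escalation will "establish a MTD recommended dose of MK-3475 in combination with lead in MK-3475 followed by the combination or concurrent afatinib/MK-3475". Section 5.1.5.2 says the phase "will establish a MTD recommended dose of MK-3475 in expansion cohorts (A +B". Section 5.1.4 says of each expansion cohort: "This treatment will start at the MTD determined in the dose de-escalation portion of this trial".

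**Schedules.** Cycles last 21 days. The footnote to Table 3 says of afatinib: "Cohort B begins in Cycle 3". Note 9 to the flow chart in 6.1 reads "For the dose de-escalation and Cohort (Arm) A (concurrent afatinib and MK-3475) both drugs will be administered", and puts the start at cycle 1. The same note has Cohort B begin with MK-3475 alone and add afatinib at cycle 3.

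**Use of toxicity.** Section 2.1 uses the expansion cohorts to define toxicity further and settle the RP2D. Section 8.1 plans descriptive counts by type and grade, and bases the choice between Cohorts A and B partly on toxicity.

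**When toxicity counts.** Section 7.1.2.6 makes patients evaluable from their first treatment with the two drugs. Section 7.5 has all adverse events reported from treatment allocation. It also treats events as on treatment from the first afatinib dose until 28 days after the last.

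**The concern.** The Cycle 1 rules suit patients who take both drugs from Day 1. In Cohort B, Cycle 1 is MK-3475 alone. The two DLT items written for diarrhea and rash attributed to afatinib (5.3, items 7 and 8) cannot arise there. Section 5.6.5 puts the onset of afatinib diarrhea generally within two weeks of first exposure, which in Cohort B falls after Day 43.

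Two things are at stake. First, 8.1 can be read as saying that de-escalation tests the lead-in schedule, which it does not. Second, the A-versus-B choice compares toxicity between cohorts whose first six weeks differ completely in combination exposure. A Cohort B patient who stops at the first response scan has had no scheduled combination treatment, while a Cohort A patient stopping then has had two combination cycles. If both simply count as treated, the lead-in could look better tolerated because exposure was shorter.

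**Working it through.** The plan states no figure on this point. The check is a day count and a side-by-side reading.

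**1. Start of the combination in Cohort B.** Two 21-day cycles come first (5.1.4), so C3D1 = 2 × 21 + 1 = Day 43. The Cycle 1 window closes on Day 21, which is 43 − 21 = 22 days earlier.

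**2. Scheduled afatinib days.** The first response scan follows cycle 2, at 6 weeks (7.1.2.6).

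| | By Day 21 (5.3 window) | By Day 42 (first scan) |
|---|---|---|
| De-escalation and Cohort A | 21 of 21 | 42 of 42 |
| Cohort B | 0 of 21 | 0 of 42 |

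**3. Who tests the lead-in schedule.** De-escalation: 0 of at most 18 patients. Cohort B: 10 patients, which is 10/38 = 26% of the maximum enrolment and 10/20 = 50% of the expansion.

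**4. The rules applied literally to Cohort B.**
- Under 5.9, a patient with 0% of afatinib in Cycle 1 and no DLT is non-evaluable and must be replaced. If the 80% is instead taken over scheduled drug only, the patient counts, but on MK-3475 alone. Neither reading assesses the combination.
- Section 10.5 calls a meeting when the last subject of each cohort completes DLT assessment. For Cohort B that is Day 21 of the last patient, 22 days before that patient's first combination dose. Patients enrolled earlier may already have started afatinib.

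**5. Toxicity start date in Cohort B.**
- 7.5, reporting: from treatment allocation, so lead-in events are included.
- 7.5, on treatment: from the first afatinib dose, Day 43, so lead-in events are left out.
- 7.1.2.6: Day 1 if first treatment means the first study drug, Day 43 if it means the first dose of the combination.

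The last two readings differ by 43 − 1 = 42 days. In Cohort A all of these dates fall at about the start of treatment, so the conflict shows only in Cohort B. Section 8.1 does not say which date its summary uses.

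**6. What precedes Cohort B.** De-escalation closes with six patients treated at the selected level (5.1.5.2), and Cohort A is completed before Cohort B opens (5.1.4, 5.2). The plan therefore puts 6 + 10 = 16 patients on the concurrent combination at that starting dose first.

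**7. Precision of a table in 10 patients.** With no events, the exact (Clopper-Pearson) 95% upper limit is 1 − 0.025^(1/10) = 0.3085, or 31%.

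**The case against.** The strongest reply is that 5.3 and 5.9 were never meant for Cohort B. DLT counts lead to action only at levels 0, -1 and -2. Section 8.1 links the 21-day observation to dose-level decisions, and 5.9 speaks of the DLT rate in a dose-level cohort. That applying 5.9 to Cohort B gives an absurd result is itself evidence of intent. Confining DLTs to dose finding is normal in a 3+3 design. On this view 8.1 is clumsy drafting, since 5.1.4 and 5.1.5.2 already carry the dose forward, and 0 of 21 days merely describes a deliberate lead-in.

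Much of this stands. De-escalation is the more natural scope, and the day counts are not an error size. Two things survive. The text does not state that scope, and 10.5 refers to DLT assessment in each cohort. Under the narrow scope, the lead-in MTD in 8.1 still has no DLT data behind it, and the A-versus-B comparison still lacks a common exposure basis.

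A reader might go further in three ways, none of which the documents support:
- **That the MTD decision is compromised.** It is made entirely on concurrent dosing, before Cohort B opens.
- **That Cohort B goes unmonitored once afatinib is added.** Adverse events are reviewed each cycle, Day 8 and Day 15 visits are recommended from C3D1 (6.1, note 1), and new related serious events are reviewed monthly (10.5).
- **That the plan has no exposure window.** Section 7.5 gives one anchored on afatinib. It would align the start of follow-up in the two cohorts, but it drops lead-in events, leaves length of exposure unequal, and is not tied to the 8.1 summary.

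**Conclusion.** The point holds as a minor one about wording and interpretation. The MTD is established for the concurrent schedule and carried forward to Cohort B, and 8.1 should not suggest otherwise. The scope of the Cycle 1 rules in 5.3 and 5.9, and of the 10.5 meeting, is not reconciled with an afatinib start on Day 43. The toxicity input to the A-versus-B choice is not aligned on combination exposure: 42 scheduled afatinib days against 0 by the first scan, and Cohort B start dates up to 42 days apart.

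This rests on nominal 21-day cycles without delays and on the stated cohort sizes. No event rates are assumed. The size of any distortion in the comparison cannot be computed, because it depends on how many Cohort B patients stop before C3D1. With 10 per cohort, each such patient is 10% of the denominator.

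**What to change.** 1. Reword 8.1 to say that the MTD is established for the concurrent schedule and carried forward to Cohort B, in line with 5.1.4 and 5.1.5.2.
2. State which phases and cohorts 5.3, 5.9 and the 10.5 meeting cover, and reconcile them with Cohort B's Cycle 3 afatinib start. The scope is for the sponsor to settle.
3. Reconcile 7.1.2.6 with the two rules in 7.5, so that Cohort B has one stated toxicity start date.
4. For the A-versus-B comparison, add a descriptive table of events meeting the existing 5.3 criteria in the first combination cycle. It would run from C1D1 in Cohort A and C3D1 in Cohort B, among patients who start the combination, with Cohort B lead-in events shown separately.

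The cost is wording plus one table. Onset dates and grades are already collected (7.5), adverse event forms are submitted after each cycle (10.9), and the C1D1 and C3D1 anchors already appear in note 1 of the flow chart. Sample size does not change. The drawbacks are that the Cohort B denominator may fall below 10 and that the table is imprecise: even 0 of 10 leaves an upper limit of 31%. If a review timed to DLT assessment is intended for Cohort B and is moved to follow combination dosing, it will come later.

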Treatment related toxicities will be managed by treatment interruptions and subsequent dose reductions of afatinib according to the schedule described in Table 6. Dose reductions will apply to individual patients only. Once the dose has been reduced, it cannot be increased later.

To prevent the development of more severe adverse events, treatment related diarrhea, nausea and vomiting or rash should be managed early and proactive as described in Section 5.6.

Products: MK-3475/Afatinib

Protocol Version 3.0
Version Date: 09/10/18

Table 6. Dose reduction scheme for Afatinib

AE Type and CTCAE Grade	Action	Dose Reduction Scheme
Events related to study drug (afatinib): 
 • Diarrhea Grade 2 persisting for 2 or more consecutive days (48 hours) despite adequate anti-diarrheal medication/hydration • Reduced renal function to \geq Grade 2 as measured by serum creatinine, proteinuria or decrease in glomerular filtration rate of more than 50% from baseline • Any drug related AE Grade ≥ 3 	
 • Pause treatment until patient has recovered to Grade ≤ 1 or baseline.¹ • Resume treatment at reduced dose according to schedule opposite. • If patient has not recovered to Grade ≤ 1 or baseline¹ within 14 days study treatment must be permanently discontinued.² 	
 • If patient was receiving 40 mg, resume treatment at a dose of 30 mg. • If patient was receiving 30 mg, resume treatment at a dose of 20 mg. • If patient was receiving 20 mg, discontinue afatinib.
Acute onset and/or unexplained worsening of pulmonary systems (dyspnea, cough, fever)	Pause afatinib while clinical assessment to exclude ILD is completed.	If ILD is ruled out as a cause of symptoms, grade symptoms and relatedness and report as AEs. If AEs are not related, resume afatinib at current dose. If AEs are drug related, follow directions in row above. If ILD is confirmed, discontinue afatinib

¹ Baseline is defined as the CTCAE Grade at the start of treatment.

² In the event that the patient is deriving obvious clinical benefit according to the investigator's judgment, further treatment with afatinib will be decided by the investigator.

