5.4 Attribution of Adverse Events

Investigators are required to assess whether there is a reasonable possibility that afatinib and/or MK-3475 caused or contributed to the adverse event. The following general guidance may be used.

- Definite – The AE is *clearly related* to the study treatment.
- Probable – The AE is *likely related* to the study treatment.
- Possible – The AE *may be related* to the study treatment.
- Unlikely – The AE is *doubtfully related* to the study treatment.
- Unrelated – The AE is *clearly NOT related* to the study treatment.

If an adverse event is attributable (either definite, probable or possible) to MK-3475 and/or afatinib that requires the drug be held the other drug may be continued if it the adverse event is not attributable to that drug (either unlikely or unrelated) with approval of the treating physician and primary investigator. Exceptions include pneumonitis and grade 2 and above enterocolitis (as defined in this protocol) where both MK-3475 and afatinib must be held.

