6.0 TRIAL FLOW CHART

6.1 Study Flow Chart

Trial Period:	Screening Phase	Treatment Cycles ^{1,9}								End of Treatment
		1	2	3	4	To be repeated beyond 8 cycles				
Scheduling Window (Days) ² :	-30 to -1	± 3	± 3	± 3	± 3	± 3	± 3	± 3	± 3	Discontinuation Visit/Safety Follow Up Visit/PFS follow up
Informed Consent	X									
Inclusion/Exclusion Criteria	X									
Demographics and Medical History	X									
Prior and Concomitant Medication Review	X	X	X	X	X	X	X	X	X	X
Trial Treatment Administration		X	X	X	X	X	X	X	X	
NSCLC Disease Details and Prior Treatment	X									
Review Adverse Events		X	X	X	X	X	X	X	X	X
Full Physical Examination	X									
Directed Physical Examination		X	X	X	X	X	X	X	X	
Vital Signs and Weight ¹²	X	X	X	X	X	X	X	X	X	
Zubrod Performance Status	X	X	X	X	X	X	X	X	X	X
Pregnancy Test – Urine or Serum β-HCG ^{3,6}	X									
PT/INR and aPTT ^{4,6}	X ⁵									
CBC with Differential ⁶	X ⁵	X	X	X	X	X	X	X	X	X
Comprehensive Serum Chemistry Panel (see	X ⁵	X	X	X	X	X	X	X	X	X
Urinalysis ⁶	X ⁵									
T3, FT4 and TSH ⁶	X ⁵		X		X		X		X	X

Trial Period:	Screening Phase	Treatment Cycles ^{1,9}								End of Treatment
		1	2	3	4	To be repeated beyond 8 <small>cycles</small>				
Treatment Cycle/Title:	Main Study Screening (Visit 1)					5	6	7	8	
Scheduling Window (Days) ²	-30 to -1			± 3	± 3	± 3	± 3	± 3	± 3	
Efficacy Measurements										
Tumor Imaging ⁷	X				X			X		
Brain Imaging (MRI or CT Scan) ¹³	X									
Tumor Biopsies/Archival Tissue Collection/Correlative Studies Blood										
Tissue Collection ¹⁰	X (must be within 60 days)				X					
EGFR Mutation Testing ⁸	X									
Correlative Studies Blood Collection ¹¹	X			X			X			X

1. In general, assessments/procedures are to be performed on Day 1 and prior to the first dose of trial treatment for each cycle unless otherwise specified. Treatment cycles are 3 weeks (21-days); however the MK-3475 treatment cycle interval may be increased due to toxicity according to the dose modification guidelines provided. If treatment cycles are increased all procedures except imaging will be completed according to the Cycle number and not weeks on treatment, imaging will be performed every 6 weeks (\pm 3 days) from the first dose of trial treatment regardless of any treatment delays. Weekly (D8 and D15 \pm 3 days) follow up visits for the first cycle when starting afatinib is recommended (when afatinib is added (Cohort A C1D1 and Cohort B C3D1)).

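### A Cycle 1 toxicity that stops afatinib for 14 days or more can drop out of the DLT count, because item 10 depends on the start of Cycle 2 and the 80% rule replaces such patients

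*Combined protocol and SAP*

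**What the plan says.** Section 5.3 sets the DLT window: "The occurrence of any of the following toxicities during Cycle 1 will be considered a DLT". Items 3, 7 and 8 require Grade 3 to last more than 3 days (72 hours) despite supportive care; Grade 4 non-hematologic events count regardless of duration. Item 10 adds a delay in starting Cycle 2 of at least "14 days due to toxicity related to afatinib and/or MK-3475". No item names the interruption or permanent stop of one drug.

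Item 9 sets evaluability: "To be evaluable for a DLT, 80% of dose must have been administered in cycle 1 unless a DLT occurred". Section 5.9 says that patients under 80% in Cycle 1 without a DLT are left out of the DLT rate and replaced. It names the two drugs together and calls them an infusion, although afatinib is a tablet.

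Section 5.4 says that when one drug must be held, "the other drug may be continued if it the adverse event is not attributable to that drug", with the approval of the treating physician and the primary investigator. Pneumonitis and enterocolitis of Grade 2 or above are exceptions; both drugs are then held.

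Table 6 (section 5.1.5.3) pauses afatinib for events that include some below DLT level, such as Grade 2 diarrhea lasting 48 hours. If the patient has not recovered to Grade 1 or baseline, "within 14 days study treatment must be permanently discontinued". A footnote lets the investigator decide otherwise where there is clear benefit.

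On timing, section 5.1.4 states "Each cycle is 21 days in length", and flow-chart footnote 1 (section 6.1) adds "however the MK-3475 treatment cycle interval may be increased due to toxicity according to the dose modification guidelines provided".

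**The concern.** MK-3475 is fixed at 200 mg at every dose level; only afatinib is de-escalated. The toxicities most relevant to the dose decision are therefore those that make a patient lose afatinib. Item 10 is meant to catch toxicity that costs treatment time without meeting a grade-and-duration threshold, but it is triggered by the start of a cycle and not by loss of a drug. If MK-3475 is given on schedule while afatinib is held, nothing says whether Cycle 2 has started. Where the hold begins early, the evaluability rule removes the patient before item 10 matters.

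A level passes with at most one DLT in six, so one or two such patients can decide the MTD. The 20 expansion patients are then treated at the dose that results.

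**Working it through.** **Plan's own figures.** Sections 5.1.5.2 and 8.1 give 9 to 38 patients. This reproduces: 3 levels × 3 = 9; 3 levels × 6 = 18; 18 + 2 × 10 = 38. The plan states no probability of passing a level, so there is none to reproduce.

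**Step 1: evaluability by day of onset.** 80% of 21 daily afatinib doses is 0.8 × 21 = 16.8, so 17 doses are needed and at most 4 may be missed. Suppose afatinib is held from Day s for 14 days and can resume on Day s + 14.

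- Onset by Day 8: the whole hold lies within Cycle 1. Doses taken = 21 − 14 = 7, or 7/21 = 33%.
- Onset on Days 9 to 17: doses taken = s − 1, that is 8 to 16, or 38% to 76%.
- Onset on Days 18 to 21: doses taken = 17 to 20, or 81% to 95%.

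If the 80% applies to afatinib, the first two groups are replaced and only the third is evaluable. If section 5.9 needs both drugs under 80%, all three stay evaluable, because the single MK-3475 infusion of Cycle 1 was given in full.

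**Step 2: does item 10 catch the evaluable group?** Cycle 2 is due on Day 22. A 14-day hold from Days 18 to 21 ends on Days 32 to 35, which is 10 to 13 days after Day 22. Item 10 is not met even if Cycle 2 waits for afatinib. For a longer hold or a permanent stop, the score depends on whether MK-3475 alone starts Cycle 2.

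**Step 3: an example the text allows.** Afatinib-related Grade 3 rash starts on Day 18 and afatinib is paused. The rash falls to Grade 2 by Day 21, so it has not exceeded 3 days and items 3 and 8 are not met. Doses taken are 17/21 = 81%, so the patient is evaluable. MK-3475 is continued on Day 22 under section 5.4. The rash is still Grade 2 on Day 18 + 14 = Day 32, when Table 6 calls for permanent discontinuation unless its benefit footnote is used. If the Day 22 infusion started Cycle 2, the score is no DLT.

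**Step 4: effect on passing a level.** With six patients and at most one DLT allowed, P(pass) = (1 − p)^6 + 6p(1 − p)^5. Let d be the rate of events already counted and m the rate of uncounted afatinib-stopping events, with no overlap. Then p = d + m if they are counted, p = d/(1 − m) if those patients are replaced, and p = d if they are scored as no DLT. Both rates are assumptions.

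For d = 0.20 and m = 0.10:
- counted: p = 0.30; 0.1176 + 0.3025 = 0.420
- replaced: p = 0.20/0.90 = 0.222; 0.2214 + 0.3795 = 0.601
- no DLT: p = 0.20; 0.2621 + 0.3932 = 0.655

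| d | m | Counted | Replaced | Scored no DLT |
|---|---|---|---|---|
| 0.10 | 0.10 | 66% | 86% | 89% |
| 0.20 | 0.05 | 53% | 63% | 66% |
| 0.20 | 0.10 | 42% | 60% | 66% |
| 0.20 | 0.20 | 23% | 53% | 66% |
| 0.30 | 0.20 | 11% | 27% | 42% |

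Each row treats all uncounted events as going one way. A real mixture would lie between the last two columns.

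**The case against.** The strongest reply is that the gap is narrow and partly a matter of reading. Nothing states that MK-3475 alone starts Cycle 2. Table 3 gives afatinib on Days 1 to 21 of each cycle, section 5.1.6 has it taken before MK-3475 on Day 1, and item 10 names both drugs. Table 6 speaks of study treatment, which could mean both drugs. This stands, and is why the point is one of reconciliation. It does not close the gap: for onset on Day 9 or later, the 14-day limit falls on Day 23 or later, after MK-3475 is due, and for Days 18 to 21 a 14-day hold escapes item 10 on either reading.

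A reader might infer that any Cycle 1 toxicity that stops afatinib is scored as no DLT whenever MK-3475 goes ahead. The documents do not support that: with onset by Day 17, item 9 and section 5.9 would normally replace the patient. Section 5.6.5 says diarrhea generally begins within two weeks of exposure, so for that toxicity replacement is the likelier route. Nor is item 10 the only item that catches short events. Item 4 has no minimum duration for laboratory values that need intervention or hospitalization, and item 5 has none for febrile neutropenia.

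Other safeguards exist: overall toxicity informs the expansion dose and RP2D, Cohort A is completed before Cohort B, and investigators confer after each cohort's DLT assessment. These soften the consequence, but the pass rule in section 8.1 still counts DLTs only.

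**Conclusion.** The point holds within limits. It concerns related Cycle 1 toxicities that stop afatinib for 14 days or more and miss items 1 to 8: chiefly persistent Grade 2 events and Grade 3 events of no more than 3 days. They can leave the DLT count through a no-DLT score (onset on Days 18 to 21, or any onset if section 5.9 needs both drugs under 80%) or through replacement (earlier onset). Both push the observed DLT rate down and favor the higher afatinib dose.

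The size cannot be fixed from the documents. At the assumed d = 0.20 and m = 0.10, the pass probability rises from 42% to 60% or 66%; at m = 0.05, from 53% to 63% or 66%. The direction does not depend on the rates.

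A further inference, that every permanent discontinuation ought to be a DLT, is not supported. Item 2 deliberately requires "Grade 4 hematologic toxicity lasting" at least 14 days, and item 4 sets its own conditions, although Table 5 can discontinue MK-3475 for events short of either.

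**What to change.** Reconcile items 9 and 10 of section 5.3 with sections 5.4 and 5.9 and Table 6:

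- Apply item 10's existing 14-day threshold to each drug separately: a related toxicity with onset in Cycle 1 that has not recovered enough to resume that drug after 14 days or more.
- Define what starts Cycle 2 when one drug is held, and whether study treatment in Table 6 means afatinib or both drugs.
- State in item 9 and section 5.9 to which drug the 80% applies.
- State that a patient under 80% because of related toxicity stays in the DLT assessment and is not replaced. Say also how a shortfall of 5 or more doses (16/21 = 76%) from a hold shorter than 14 days is scored.

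Do not turn every permanent discontinuation under Table 5 or Table 6 into a DLT. That would override items 2 and 4. It would also make the definition differ by dose level, because Table 6 stops afatinib at 20 mg for events that lead only to a reduction at 30 or 40 mg.

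The cost is a few sentences. The rule becomes somewhat more conservative, and late-onset events take up to 14 more days to classify: onset on Day 21 would be settled by Day 35, within the Day 22 + 14 = Day 36 that item 10 already implies. The change touches only what is counted; dose-modification and patient-care rules stay as written, apart from the clarification that Table 6 needs.
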